Children with cyanotic heart disease, “blue babies”, have chronically low oxygen levels and are at particular risk for death and poor outcomes because of their reduced ability to provide adequate oxygen to the body and brain. These infants should ideally maintain hemoglobin or red blood cell levels greater than 13 g/dL or a hematocrit >40% (Strauss 1991, Roseff 2002), to deliver adequate amounts of oxygen to the body. Healthy infants often experience a drop in their red blood cell level during their first few months of life, as part of the body's normal maturation process. Children with cyanotic heart disease experience this same phenomenon, but are also exposed to additional risks such as critical illness and surgical procedures. Thus, newborns with cyanotic heart disease may require blood transfusions as part of their care in order to provide adequate oxygen to the body. Although rare, the adverse outcomes due to transfusions can be devastating to this population. These complications include transmitted infections, transfusion reactions, additional hospitalizations, and production of antibodies that could complicate heart transplant if needed in the future. Epoetin alfa (EPO) and iron stimulate red blood cell production. Studies with EPO have been done in premature infants and children prior to surgery in order to assess the drug's ability to increase red blood cell levels [1-4]. They show that early administration of EPO has reduced the use of blood transfusions. We seek to investigate, through a prospective randomized controlled trial, if EPO and iron make a clinically significant difference in the number of transfusions given to infants with cyanotic heart disease. We hypothesize that prophylactic EPO and iron may prevent and/or decrease the amount of blood transfusions needed in this population.

A2 Primary Hypothesis

We hypothesize that prophylactic EPO and iron can prevent and/or decrease the amount of blood transfusions needed in this population.

A3 Purpose of the Study Protocol

The purpose of this study protocol is to provide a guide and timeline for the completion of this prospective randomized controlled trial.

B Background

B1 Prior Literature and Studies

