There are centers in the United States that have developed protocols using erythropoietin to minimize blood product transfusions before and after surgery, also referred to as "bloodless surgery"[4]. There have been retrospective studies evaluating the success of these protocols, but there are no randomized controlled prospective studies that have studied the effects of erythropoietin in patients with cyanotic heart disease in regards to transfusion prevention. There have also been multiple studies looking at the efficacy of EPO in the premature infant population (Donato 2005). In these studies, EPO has been shown to prevent blood transfusions. However, these findings did not represent a clinically significant difference for the study population in the long term. The clinical significance is enhanced in our study population, because blood transfusions may have significant implications for transplant candidacy in the future and transplant complications if needed. Last, there is a study involving infants and children with craniosynostosis showing that EPO is safe and can reduce the number of blood transfusions in a surgical group that has high risk for bleeding (Fearon 2001).

C Study Objectives

C1 Primary Aim

Congenital cyanotic cardiac patients require higher hemoglobin concentrations for optimal oxygen delivery. Prophylactic erythropoietin can prevent and/or decrease the amount of blood transfusions needed prior to surgery. We seek to investigate if erythropoietin makes a clinically significant difference in the number of transfusions given to these patients and the morbidity associated with it during the period in which the subjects will be active in the study (from baseline to 14 weeks post initial injection). The primary aim will be assessed when all subjects have completed week 14 or discontinued early.

C2 Secondary Aim

We will also look to see if administering erythropoietin makes a clinical significance in the following outcomes during the period in which the subjects will be active in the study

(from baseline to 14 weeks post initial injection): weight gain, oxygen saturations, length of initial hospital stay, and hospital readmissions (related to failure to thrive or cyanosis).

C3 Rationale for the Selection of Outcome Measures

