Epoetin alfa is a recombinant form of human erythropoietin used to stimulate erythropoiesis. Iron then helps support proper heme formation with the production of hemoglobin. EPO is administered by injections. Iron will be administered orally or intravenously if orals are not tolerated.

3.b Treatment Regimen

Experimental: Epoetin alfa and iron supplements:

Patients in the treatment group will receive weekly erythropoietin injections for 6 weeks starting before 8 weeks of age (at least one week after their surgery) at 500 units/kg/injection (SQ or IV).(Donato 2005 & Maier 2002) Oral ferrous sulfate 3 mg/kg/day of elemental iron will be given throughout the study if enteral feeds are tolerated which is an accepted treatment for anemia and prevention of anemia. If oral iron cannot be tolerated and there is laboratory evidence of iron deficiency, intravenous iron (either Iron sucrose or Iron dextran) will be used to replace iron stores based on the calculated iron deficit: Total replacement dose (mg of iron) = 0.6 x weight (kg) x [100 -

(actual Hgb /Desired Hgb x 100)]. This will be given in 5-7 mg/kg every day until the total replacement dose is achieved.

Iron studies (Serum iron, ferritin, total iron binding capacity) will be obtained at baseline and at week 14 with the final lab draw. If intravenous iron is used for replacement, iron studies will be repeated after replacement to ensure adequate iron stores.

All injections will be administered by a member of the subject's care team (bedside nurse, nurse practitioner, or physician) with a weekly visit in the cardiology clinic or in the hospital if the infant remains hospitalized after being dispensed by the research pharmacist.

A complete blood count will be obtained in the hospital prior to initiation of treatment for baseline measurements and to confirm eligibility if not obtained within 48 hours prior to the 1st injection as a part of the patient's standard of care. It will be repeated weekly (weeks 2-7) whether inpatient or outpatient, to confirm that there is no over-shoot with a hematocrit >45%. Labs will be reviewed prior to treatment. Treatment will be held for hematocrit levels >45%. There will be another lab drawn 14 weeks after the initial injection. Outpatient visits and lab draws will be paid for by the study grant. All labs will be analyzed by the Rady Children's Hospital Laboratory. The study drug will be provided by the study grant.

Observational Control:

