An observational group will be used as a control. Thus to keep the integrity of the study with minimal bias, strict adherence to the blood transfusion guidelines as listed above is required.

Patients in the control group will have no injections given. This group will receive oral ferrous sulfate 3 mg/kg/day of elemental iron for 6 weeks starting before 8 weeks of age (at least one week after their surgery).

If oral iron cannot be tolerated and there is laboratory evidence of iron deficiency, intravenous iron (either Iron sucrose or iron dextran) will be used to replace iron stores based on the calculated iron deficit: Total replacement dose (mg of iron) = 0.6 x weight (kg) x [100 - (actual Hgb /Desired Hgb x 100)]. This will be given in 5-7 mg/kg every day until the total replacement dose is achieved.

Iron studies (Serum iron, ferritin, total iron binding capacity) will be obtained at baseline and at week 14 with the final lab draw. If intravenous iron is used for replacement, iron studies will be repeated after replacement to ensure adequate iron stores.

A complete blood count will be obtained in the hospital prior to initiation of treatment for baseline measurements and to confirm eligibility if not obtained within 48 hours prior to enrollment as a part of the patient's standard of care. A repeat CBC will be obtained at week 7 and 14 of the subject's participation in the study which will be provided by the study grant. A CBC may be obtained earlier if indicated by the subject's care team as a

part of standard of care. All labs will be analyzed by the Rady Children's Hospital Laboratory.

3.c Method for Assigning Subjects to Treatment Groups

After a study subject has been enrolled, a 2-digit number will be assigned. Based on the number and a pre-randomized allocation scheme devised by the biostatistics department, the subject will be placed into the treatment arm or the control arm of the study.

3.d Preparation and Administration of Study Drug

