[name] – Principal Investigator (attending cardiologist/intensivist at RCHSD) – responsible for recruitment, data collection and analysis, as well as manuscript preparation.

[name] (Attending cardiologist at Children's Hospital of Pittsburgh) – will assist in analysis of deidentified data and manuscript preparation.

[name] (Attending cardiologist at Children's Hospital of San Antonio)– will assist in analysis of deidentified data and manuscript preparation.

[name], PhD (attending cardiologist at RCHSD)– will assist in recruitment therapy administration, in data collection, analysis, and manuscript preparation.

[name] RN, MSN, ACNP- (Nurse Practitioner at RCHSD) – will assist in recruitment, therapy administration, in data collection, analysis, and manuscript preparation.

[name] (Attending neonatologist at RCHSD) -- will assist in recruitment therapy administration, in data collection, analysis, and manuscript preparation.

[name] (Pediatric Resident, UCSD) –will assist in recruitment, therapy administration, data collection, analysis and manuscript preparation.

[name], MS – Research Coordinator – responsible for all regulatory/IRB documents and communications pertaining to the study.

J4 Subject Stipends or Payments

There is no stipend or monetary benefits to the patient or their families.

J5 Study Timetable

This study is projected to take 4 years. 2 to 2.5 years for recruitment of study subjects and obtain all necessary data. 1.5 to 2 years for statistical analysis and manuscript preparation.

K Publication Plan

After the study and analysis is complete, we plan to publish the data to a journal that is well recognized in the field of congenital heart disease.

L Attachments

L1 Tables

**Table 1
 Treatment Group**

Tests and Procedures	Baseline (one week post op/cath, ≤ 48 hours prior to 1 st injection)	Week 1 (1 week post op)	Week 2*	Week 3*	Week 4*	Week 5*	Week 6*	Week 7*	Week 14
Review eligibility	X								
Informed Consent	X								
Physical Exam including Saturation	X	X	X	X	X	X	X	X	X
Epogen Injection		X	X	X	X	X	X		
Iron		X and ongoing for 12 weeks							
CBC Lab Draw	X		X	X	X	X	X	X	X
Iron Studies	X		If needed after iron replacement therapy						X

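### Oral iron duration is inconsistent: controls get 6 weeks in the regimen text but 12 weeks in Table 2, and only the tables make the two arms equal

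*Combined protocol and SAP*

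**What the plan says.** Section E3 3.b, Treatment Regimen, sets the oral iron course separately for each arm, at the same dose of 3 mg/kg/day of elemental iron.

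- EPO arm: iron "will be given throughout the study if enteral feeds are tolerated". No number of weeks is given.
- Control arm: "This group will receive oral ferrous sulfate 3 mg/kg/day of elemental iron for 6 weeks starting before 8 weeks of age".

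The schedules in L1 give a third duration. The iron row of Table 1 (treatment) and the iron row of Table 2 (control) carry the same entry, starting at Week 1: "X and ongoing for 12 weeks".

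D4 repeats the daily dose but gives no duration. The rule for switching to intravenous iron is the same in both arms. Transfusions are counted over the period of active participation, defined in C1 and again in G4 as "from baseline to 14 weeks post initial injection".

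**The concern.** Iron is not a neutral background treatment here. The abstract (A1) states: "Epoetin alfa (EPO) and iron stimulate red blood cell production". Section 3.b describes the oral iron course as one "which is an accepted treatment for anemia and prevention of anemia". Hematocrit drives the transfusion rules in E2 2.i: below 30% is an absolute indication, and below 40% is part of every relative one. Transfusion is the primary outcome.

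If the regimen text is followed, the arms differ in two anti-anemia treatments rather than one during the later part of the outcome window. A lower transfusion rate on EPO could then reflect longer iron as well as EPO, and the analysis planned in G4 cannot separate the two. If the tables are followed, iron is balanced and the problem does not arise. So the contrast being tested depends on which page is followed.

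**Working it through.** **Inputs**

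- Dose: 3 mg/kg/day in both arms (E3 3.b), so 3 × 7 = 21 mg/kg per week.
- Control duration: 6 weeks (3.b) or 12 weeks (Table 2).
- EPO-arm duration: throughout the study (3.b) or 12 weeks (Table 1).
- Length of the study for one infant: follow-up is 14 weeks (E1; also C1 and G4). Counting from the first injection to 14 weeks gives 14 weeks. Counting from the Week 1 visit to the Week 14 visit gives 14 − 1 = 13 weeks. The 3.b wording for the EPO arm is therefore taken as 13 to 14 weeks. This is an inference.

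**Planned oral iron at full adherence** (21 mg/kg × weeks)

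- 6 weeks: 21 × 6 = 126 mg/kg
- 12 weeks: 21 × 12 = 252 mg/kg
- 13 weeks: 21 × 13 = 273 mg/kg
- 14 weeks: 21 × 14 = 294 mg/kg

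**Gap between arms, by which source is followed**

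| EPO arm follows | Control arm follows | EPO, mg/kg | Control, mg/kg | Gap, mg/kg | Gap, weeks |
|---|---|---|---|---|---|
| 3.b text | 3.b text | 273 to 294 | 126 | 147 to 168 | 7 to 8 |
| Table 1 | 3.b text | 252 | 126 | 126 | 6 |
| 3.b text | Table 2 | 273 to 294 | 252 | 21 to 42 | 1 to 2 |
| Table 1 | Table 2 | 252 | 252 | 0 | 0 |

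**What the comparison shows**

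1. Within the control arm, text and table differ by a factor of two (126 versus 252 mg/kg). Both are explicit numbers of weeks, so this conflict is firm.
2. Within the EPO arm, text and table differ by only 1 to 2 weeks, and only once the text has been converted to weeks.
3. The shortest duration anywhere is 6 weeks, so every combination gives both arms the same iron for the first 6 weeks, which is also the length of the injection course. Any gap opens at about week 7.
4. From then to week 14 the infants are still in the period over which transfusions are counted.

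The documents give no figure for the effect of additional weeks of oral iron on hematocrit or on transfusion in these infants, so the calculation stops at planned dose. The sample size and power in G1 and G4 do not depend on iron duration and are unaffected.

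**The case against.** The strongest reply is that equal iron was probably intended. Both tables give 12 weeks. The control sentence in 3.b closely follows the wording that sets the EPO injection course, which is also 6 weeks, so the number may simply have been carried over. The EPO-arm wording could be a loose way of describing the 12 weeks in Table 1. These points are fair and make the balanced reading plausible. They do not settle it: the 6-week statement is intact, explicit and current, and nothing in the available text says that the tables override the regimen section.

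It can also be said that a difference would not go unseen. Serum iron, ferritin and total iron binding capacity are measured at baseline and week 14 in both arms (3.b, F2). Section 3.e has the research team record iron compliance on the case report form, and F6 lists medication compliance among the data collected. This stands, and it means that little new data collection is needed. It does not remove the conflict, because these records would reveal unequal iron but not prevent it.

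A further reply is that A2 pairs iron with EPO ("prophylactic EPO and iron can prevent and/or decrease the amount of blood transfusions"), so longer iron might be part of the experimental package. The documents do not say so. Controls are also given iron, both tables make it equal, and C1 frames the aim around erythropoietin alone ("Prophylactic erythropoietin can prevent and/or decrease the amount of blood transfusions needed prior to surgery").

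**Conclusion.** The plan is wrong as written on this point and should be corrected. The firm part is the control arm: 6 weeks in the text against 12 in Table 2. The EPO-arm mismatch is smaller (1 to 2 weeks) and may be only loose wording. At most, following the text would give EPO infants about 7 to 8 more weeks of iron, or 147 to 168 mg/kg at full adherence, all of it after the first 6 weeks and within the primary outcome window. Following the tables gives no difference.

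A reader might infer more than this. One inference is that the EPO arm is definitely assigned 14 weeks of iron; 14 is only the upper end of an inferred range. Another is that the primary comparison is already confounded in favour of EPO. The documents do not show which duration is used in practice, so an imbalance is possible but not established, and longer iron could favour EPO without any certainty that it would. Nor can the planned-dose gap be read as a size of bias.

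The result assumes full adherence to oral iron in both arms. Most of the consent form and part of the case report form are not available here. A duration stated there might show the intention, but would not remove the conflict between 3.b and Table 2.

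**What to change.** State the same iron duration for both arms in E3 3.b. Twelve weeks is the natural choice because it agrees with both tables. Another single duration would also serve, provided that both tables are corrected to match. Equality between the arms is the essential part. Check that the consent form states the same duration.

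From the iron compliance already recorded under 3.e, report days on iron by arm alongside the baseline and week 14 iron studies, so that any difference already incurred is visible. If the compliance entry does not capture when iron stopped, one date field would be needed.

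The cost is a short amendment. If the tables describe current practice, only the text in 3.b changes. If 6 weeks has been the practice for controls, moving to 12 adds up to 6 weeks of oral iron for them (252 − 126 = 126 mg/kg). If EPO infants have been treated to the end of the study, 12 weeks shortens their course by 1 to 2 weeks (21 to 42 mg/kg).

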Informed consent will be obtained by one of the research study members after the initial surgical or catheterization procedure. Each member is well informed of the study objectives, procedures, risks, benefits, physiology of the disease process and mechanism of how the treatment works. The informed consent will be obtained from the patient's parent in a private setting. Details of the study will be presented, and ample time will be given to answer any questions. The parent will have until the eligibility period expires based on the exclusion criteria outlined above to be included in the study. Consent will be obtained in the primary language of the parent. English and Spanish versions of the consent documents will be available and official translators will be used as appropriate. An appropriate official translator will be used during the entire duration of the participant in the study. Informed consent and HIPPA authorization will be documented with the study forms that have been drafted and approved for use in the study and will be kept in a master research file for the duration of the study in a secure area, in a locked drawer by the study team. It will be made clear to the parents that participation in the study is voluntary and that decision to be included or excluded will not compromise the standard of care that the patient deserves. Patients who meet all inclusion criteria except the hematocrit of <40% will be approached and consented, but will not be formally enrolled and randomized into a study group (control or EPO) unless their hematocrit reaches <40% during their eligibility period.

2.d Randomization Method

Study subjects will be randomized 1 to 1 by an algorithm determined by the biostatistician involved. After a study subject has been enrolled into the study, a 2-digit number (1-60) will be assigned. Based on the subject number and predetermined randomization provided, a research pharmacist will dispense the study drug if the subject is enrolled in the intervention arm. This study will not be blinded.

2.e Risks and Benefits

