The research team will review the visits data at least once a week to monitor for adverse events, compliance, and progress of the study. The research team will meet with the Principal Investigator weekly with a report of adverse events and serious adverse events.

ii Institutional Data and Safety Monitoring Board

The UCSD Data and Safety Monitoring Board (DSMB) has been identified through the Clinical and Translational Research Institute. The DSMB is composed of experts in biostatistics, clinical trial design, and medicine. The DSMB will meet as subjects are enrolled in increments of 5 or annually (whichever is more frequent). . The DSMB will be responsible for monitoring the safety of the study.

5.c Definitions of Adverse Events

The FDA Final Rule on Investigational New Drug Safety Reporting Requirements [<http://edocket.access.gpo.gov/2010/pdf/2010-24296.pdf>] defines the following terms:

- **Adverse Event**: Any untoward (e.g. unfavorable, negative, or harmful) medical occurrence associated with the use of a drug in humans, whether or not the event is considered drug related. An event can be any unfavorable and unintended sign, symptom, or disease temporally associated with the use of the product.
- **Suspected Adverse Reaction**: Any AE for which there is a reasonable possibility that the drug caused the event, meaning the event is possibly, probably, or definitely related to the study drug.
- **Adverse Reaction**: An AE for which there is a greater degree of certainty regarding causality; meaning the event is probably or definitely related to the study drug. Adverse reactions are a subset of Suspected Adverse Reactions.

5.d Classification of Events

Monitoring adverse events requires that they be classified as to potential relationship, severity, and of the study drugs, all of which drive the reporting process.

i Relationship

Relationship assessment is required in clinical investigations to help determine which events require expedited reporting. The following criteria will be used to determine relationship:

1. **Not Related**: The event is clearly related to other factors, such as the subject's clinical state, or non-study drugs or interventions.
2. **Possibly Related**: The event follows a compatible temporal sequence from the time of administration of the study drug, but could have been produced by other factors such as the subject's clinical state or non-study drugs or interventions.

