- Decreases or increases in the production of other blood cell types
- High blood sugar
- Insomnia
- Depression
- Trouble swallowing
- Low potassium levels
- Weight loss

5.e Grading of Adverse events

Adverse events will be graded based on the “Common Terminology Criteria for Adverse Events (CTCAE) Version 4.0” as published by the U.S. Department of Health and Human Services, National Institute of Health, and National Cancer Institute. This can be found at: http://evs.nci.nih.gov/ftp1/CTCAE/CTCAE_4.03_2010-06-14_QuickReference_8.5x11.pdf

5.f Data Collection Procedures for Adverse Events

In this trial, a primary safety concern as well as one of the secondary end points is to capture and compare suspected adverse reactions and adverse reactions associated with epoetin alfa administration. In addition, following standard clinical trial procedures, information on other adverse events and patient-reported symptoms will be collected.

Adverse Events will be assessed at baseline and at each study visit. Subjects and families will be encouraged to report adverse events to study personnel as soon as the event occurs, rather than waiting for scheduled visits. Patient reported symptoms will be captured at each of these time points and will be documented by the study coordinators or investigators. Assessments at baseline will be obtained while the subject is not taking any study drug and is essential to accurate assessment of drug effects. Laboratory monitoring will be conducted to assess drug safety as outlined in *Table 1 and Table 2*. Abnormal values will be used to adjust study drug dosage (intervention will be held for hematocrit levels >45%), and will not be reported separately as adverse reactions or adverse events. However, analysis of safety at the end of the trial will encompass adverse reactions, other adverse events, and these laboratory abnormalities, for a comprehensive assessment of the safety profile of the study drugs.

5.g Reporting Procedures

The research investigators will report all adverse events, regardless of expectedness and relationship to the study drug according to the following timeframes:

Classification	Expectedness	Relatedness	Reporting Timeframe
----------------	--------------	-------------	---------------------

Serious: Fatal life Threatening	Unexpected	Related	Within 10 calendar days of first knowledge of event to the IRB

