G3 Analysis Plan

All primary analyses for efficacy will be performed on an intention-to-treat basis. All subjects will be analyzed according to their group assignment regardless of actual treatment received. In addition, both groups will be compared for safety at the end of the study by comparing adverse events and rates of adverse events. In the safety analysis, subjects will only be included if they actually received treatments in that group. (i.e. if a patient on the EPO arm did not get EPO, they should not be included in the analysis of safety in that arm).

G4 Statistical Methods

All data will only be gathered during the period in which the subjects will be active in the study (from baseline to 14 weeks post initial injection).

For the primary aim, we will compare the number of blood transfusions (one 10 ml/kg aliquot = 1 transfusion) between the two groups with a two-proportion z test. With $n = 20$ subjects per group, this test will have 80% power at the $\alpha = 0.05$ significance level to detect a difference. The primary aim will be assessed when all subjects have completed week 14.

We will compare weight gain and the change in oxygen saturation between baseline measurements and the 6 week follow-up with a two sample t-test. We will also use a linear mixed effects model, with a random intercept included to account for within subject correlation, to determine differences in the longitudinal trends in weight and oxygen saturation between groups. The length of the initial stay will be compared between groups with a two-sample t-test. We will treat the number of re-admissions (in regards to failure to thrive and cyanosis) as a categorical variable, and use Fisher's exact test to determine if there is a difference between EPO and control group readmission counts. We will consider the Mann-Whitney U test as a robust alternative to the two-sample t-test if the assumptions of the t-test are not met by the data.

With a sample size of $n = 20$ subjects per group, the t-tests described above will have 80% power at the $\alpha = 0.05$ level to detect an effect size equal to 0.91 times the common standard deviation. For weight change, assuming that the standard deviation of weights at baseline and the 6 week follow-up equal 1.22 and 1.53 (respectively), and assuming a

moderately high correlation between weight measurements within child of $\rho = 0.70$, this translates to a detectable difference of 1.00 kgs.

G5 Missing Outcome Data

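### The one safety comparison named as a secondary end point counts reactions attributed to epoetin alfa, which controls cannot have; 5.f should be aligned with the all-event comparisons in G2 and G3.

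*Combined protocol and SAP*

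**What the plan says.** **The end point.** F5 5.f describes a primary safety concern that is also a secondary end point: to "capture and compare suspected adverse reactions and adverse reactions associated with epoetin alfa administration". C2 lists no safety outcome among the secondary aims, and G4 gives no test for one.

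**The definitions.** Under 5.c, a suspected adverse reaction is an event with a reasonable possibility of drug causation, "meaning the event is possibly, probably, or definitely related to the study drug". An adverse reaction is the more certain subset. Even the weakest related category in 5.d.i is tied to dosing: "The event follows a compatible temporal sequence from the time of administration of the study drug".

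**Exposure and blinding.** E3 3.b states: "Patients in the control group will have no injections given". Controls do receive iron: "This group will receive oral ferrous sulfate 3 mg/kg/day of elemental iron for 6 weeks". E2 2.d states: "This study will not be blinded".

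**The other safety comparisons.** 5.f adds that "information on other adverse events and patient-reported symptoms will be collected", and that the end-of-trial safety analysis will cover reactions, other events and laboratory abnormalities. G2 compares adverse event rates between the arms for the DSMB and plans a safety look after 10 patients per arm have completed. G3 compares the groups at the end by "comparing adverse events and rates of adverse events". G2 and G3 do not restrict these comparisons to events judged related.

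**The concern.** A between-arm comparison is informative only if the outcome can occur in both arms and is judged in the same way in both. An epoetin-attributed reaction meets neither condition. A control infant cannot have one, and in the EPO arm the count depends on a causal judgement made with the arm known. Fever, vomiting or a clot can occur in any infant with this disease, but on this end point such an event can count in one arm only.

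An analyst looking for the prespecified safety end point would find this one. An apparent excess could be reported as harm when epoetin adds no risk. A count of zero would say something about the EPO arm alone and nothing about the difference between arms. The documents would also hold two different safety comparisons, and the weaker one carries the end-point label.

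**Working it through.** The documents give no rate, test or power for safety, so there is no stated figure to reproduce. Fisher's exact test is used here for illustration.

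**Inputs from the documents**
- Minimum 20 infants per arm, up to 60 in all (G1), randomised 1:1 (E2 2.d).
- No epoetin in controls (E3 3.b), so the control count on this end point is 0.
- Scheduled visits (F2): EPO arm, baseline + weeks 1 to 7 + week 14 = 1 + 7 + 1 = 9; control arm, baseline + week 7 + week 14 = 3.

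**Assumptions, not in the documents**
- Epoetin has no effect, and a proportion b of infants in each arm has an event.
- A share f of the EPO-arm events is labelled related.

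**Step 1: how few attributed reactions look significant.** With x of n against 0 of n, the two-sided Fisher p is 2 × C(n, x) / C(2n, x).
- 3/20 v 0/20: 2 × 1,140 / 9,880 = 0.23
- 5/20 v 0/20: 2 × 15,504 / 658,008 = 0.047
- 6/30 v 0/30: p = 0.024

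At 20 per arm, five attributed reactions are enough; three are not.

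**Step 2: how often that happens with no drug effect.** The EPO-arm count is Binomial(20, b × f), so the chance is P(X ≥ 5).

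| Event rate b, both arms | f = 25% | f = 50% | f = 75% | f = 100% |
|---|---|---|---|---|
| 20% | 0.3% | 4.3% | 17% | 37% |
| 30% | 1.4% | 17% | 48% | 76% |
| 50% | 9.5% | 59% | 92% | 99% |

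For example, b = 30% and f = 50% give a labelled-event probability of 0.15 and a 17% chance of five or more. The result runs from under 1% to near certainty, depending on b and on the labelling share.

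**Step 3: the same null with all events counted.** With equal rates of 20% to 50% in both arms, a two-sided Fisher test at 20 per arm is falsely positive 2.0% to 2.5% of the time.

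**Step 4: what a null result would mean.** With no attributed reactions in 20 EPO infants, the one-sided 95% upper bound is 1 − 0.05^(1/20) = 13.9%. That is a single-arm statement.

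**Step 5: what the all-event comparison can do.** Fisher power at 20 per arm, under assumed rates, is 19% for 20% v 40%, 41% for 20% v 50%, and 74% for 10% v 50%. It is a fair comparison but a weak one.

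**The case against.** The strongest reply is that the safety comparison is already handled. G2 and G3 both compare adverse events between arms without regard to attribution, the end of 5.f widens the final safety analysis, and no stopping or DSMB decision rests on the sentence at issue. That stands. A reader might infer that the trial cannot show harm or safety at all; the documents do not support this.

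It can also be said that 5.f is a data-collection section that names no arms or test, and that its wording could mean events known to be associated with the drug, such as the 5.d.iii list that the case report form records as a checklist. That reading is possible. However, 5.f uses the two terms that 5.c defines by relatedness, and it calls the comparison an end point, so the text needs settling.

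Three further limits stand:
- The zero holds for attribution to epoetin alfa, which 5.f names. 5.c and 5.d.i refer only to the study drug, and under that wording a control could have an iron-related reaction. E3 3.d mentions an empty syringe, which must be reconciled with the no-injection statement in 3.b; either way controls get no epoetin.
- A reader might infer that real harms, such as clots, would routinely leave the end point as not related. 5.d.i reserves that category for events clearly due to other factors. An event with compatible timing that other factors could explain is possibly related. Misclassification can occur, but the rule leans towards counting.
- A reader might infer that randomisation fully protects the all-event comparison. It does not: G3 drops EPO-arm infants who received no EPO, and 5.f assesses events at visits, of which there are 9 scheduled against 3.

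**Conclusion.** The point holds for the end point named in 5.f and for its conflict with G2 and G3. As a between-arm comparison that end point is not valid: the control count is fixed at zero, and the EPO-arm count depends on open-label attribution. Five attributed reactions among 20 EPO infants give p = 0.047 whether or not epoetin does anything. With no drug effect and a 30% event rate, the chance of that runs from 1.4% to 76% as the labelling share goes from 25% to 100%. The event rates, labelling shares and choice of Fisher's test are assumptions; the structural zero follows from the text. The trial's overall safety assessment does not depend on this end point, so the correction is worth making but limited in reach.

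**What to change.** Reword the 5.f sentence so that the comparative safety end point is the proportion of infants in each arm with adverse events, overall and by 5.d.iii type, whatever the judged relationship, consistent with G2 and G3. Then:

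- Report drug-attributed reactions descriptively, within the EPO arm only.
- Do the same for events that in practice only injected infants can have. The 5.d.iii list includes injection site reactions and antibodies to EPO; comparing these between arms would bring the structural zero back.
- State next to the end point that adverse events are assessed at 9 scheduled EPO-arm visits against 3 for controls, so event rates must be read with unequal ascertainment in mind. Note also that the G3 safety population is defined by treatment received.
- For consistency, list safety in C2 and name its method in G4. At this sample size, estimates with confidence intervals will say more than tests.

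The cost is a few sentences. 5.f already collects other adverse events as well as reactions, so no extra patients, visits or data are needed. The rewording does not remove the visit imbalance; it only makes it explicit.
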